4.6.2 Other Safety Variables

Other Safety Variables are listed below:

- OST examination
- OHT examination
- Incidents

OST Examination

The OST examination will be accomplished by direct observation and palpation, using retraction aids as appropriate, and will include examination of the oral labial mucosa (including lips), buccal mucosa, and mucogingival folds, gingival mucosa, hard palate, soft palate, tonsillar area, pharyngeal area, tongue, sublingual area, submandibular area and salivary glands. The results of the examination will be recorded in the eCRF as either normal or abnormal with details of any abnormalities. Any abnormality or worsening of a pre-existing condition observed by the clinical examiner or reported by the subject from the OST examination carried out at Screening will be recorded as an AE.

OST examinations will be performed at Screening and before and after each on-site tooth brushing at Day 0, Day 7 and Day 28.

OST will be summarized (number of subjects and percentages with abnormalities, without abnormalities or OST not examined) by study product groups in [Table 14.3.4.1](#) for all subjects in Safety Population. In addition, OST will be summarized by shift table ([Table 14.3.4.2](#)) comparing normal/abnormal results of pre-brushing to post-brushing at each visit. OST examinations will be listed ([Listing 16.2.9.1](#)) for all randomized subjects.

OHT Examination

Where possible, the OHT examination should be conducted by a single dental examiner or clinically qualified designee for all subjects. Examination of the oral hard tissues (all facial, lingual/ palatal, mesial/distal and occlusal surfaces) will be accomplished by direct/indirect observation, using retraction aids as appropriate. Enamel irregularities, tooth fracture,

defective/faulty restorations (all direct & indirect restorations including fixed/removal prostheses), carious lesions, non-cariou hard tissue loss (abrasion, attrition, abfraction and erosion), tooth staining and any other hard tissue irregularity (e.g. hypo/hypermineralisation, decalcification) will be recorded. Observations will be recorded as either absent or present, and conditions noted as present will be described in the eCRF. Any abnormality or worsening of a pre-existing condition observed by the clinical examiner or reported by the subject from the OHT examination carried out at Screening will be recorded as an AE. Findings from this Screening examination will be used to determine subject eligibility.

OHT examinations will be performed at Screening and at Visit 4 Day 28, following the post-brushing OST examination.

OHT will be summarized (number of subjects and percentages with abnormalities, without abnormalities or OHT not examined) by study product group in [Table 14.3.4.3](#) for all subjects in Safety Population. OHT examinations will be listed ([Listing 16.2.9.2](#)) for all randomized subjects.

Incidents

All study products supplied are for use only in this clinical study.

A study product incident is any malfunction or deterioration in the characteristics and/or performance of a device as well as any inadequacy in the labeling or the instructions for use which, directly or indirectly, might lead to or might have led to the death of a subject/user/other person or to a serious deterioration in his/her state of health.

All Incidents will be listed in [Listing 16.2.9.3](#). In the event that there is nothing to report, a null listing will be produced.

4.7 Analysis of Other Variables

Additional/Exploratory endpoint for this study is to analyze the repeatability of dental plaque scoring.

The clinical examiner selected for this study will have demonstrated their ability to replicate their own scores (intra-examiner repeatability) on a tooth site-by-tooth site basis. Given both the RPI and the TPI allow accurate repeat assessment, repeat assessments will be performed for both clinical measures throughout the treatment period (Visits 2 to 4) to monitor consistency of scoring.

One repeat assessment will be completed for each clinical index on each clinical assessment day (one in the morning, one in the afternoon), alternating between pre- and post-brushing assessments for each index. Repeatability assessments should be separated by a minimum of 10 minutes and, where possible, the clinical examiner should assess a different subject in the intervening period. The examiner should not have sight of their previous scores when carrying out a repeat assessment.

‘Repeat’ subjects will be selected from those in attendance on a particular study day.

The repeat dental plaque assessments (for both RPI and TPI indices) will be compared to the original assessments. Repeat assessments will not be used in any efficacy analyses.

The first and repeat plaque assessments on each tooth site will be cross tabulated. A weighted kappa coefficient (κ), along with the 95% CI will be calculated to assess the intra-examiner reliability.

Fleiss-Cohen weighted kappa will be calculated for the repeatability analysis. Reliability will be deemed

- excellent if $\kappa > 0.75$;
- fair to good if $0.4 \leq \kappa \leq 0.75$;
- poor if $\kappa < 0.4$.

A $\kappa \geq 0.6$ will be considered indicative of good repeatability across the study period.

Repeatability analysis will be conducted on RPI Repeatability and TPI Repeatability Populations.

Results for RPI scoring repeatability will be presented in [Table 14.2.3.1](#). Results for TPI scoring repeatability will be presented in [Table 14.2.3.2](#).

5 Changes to the Protocol Defined Statistical Analysis Plan

Any changes from the originally planned statistical analysis specified in the protocol are outlined in [Table 5-1](#).

Table 5-1 Changes to Protocol Defined Analysis Plan

Protocol	Reporting & Analysis Plan	
Statistical Analysis section	Statistical Analysis Plan	Rationale for Changes
12.3 Definition of Analysis Populations The Repeatability population will comprise all subjects who have a repeat clinical efficacy assessment at any visit.	4.7 Analysis of Other Variables Repeatability analysis will be conducted on RPI Repeatability and TPI Repeatability Populations.	Repeatability Population will be separated for each index, in order to minimize the number of missing records caused by the fact that the subjects have repeated assessments for only one of the indices.
12.3.5 Secondary Analyses In this section it is noted that Plot of change from baseline for Days 7 and 28 will be created.	N/A	It was decided that the Plots of change from baseline for Days 7 and 28 will not be produced.
12.3.5 Secondary Analyses In this section it is noted that Box Plots of Actual Values for Days 0, 7 and 28 will be created.	N/A	It was decided that the Box Plots of actual values for Days 0, 7 and 28 will not be produced.

6 Attachment 1: List of Data Displays

GSKCH_212224_TFL
List_Amendment_1_Fin

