To ensure study subjects demonstrate the required propensity for plaque formation, only subjects with Day 0 pre-brushing mean RPI_{gingival/interproximal} ≥ 0.6 will be randomized to study treatment (Visit 2). Interproximal and gingival margins were chosen due to the unlikelihood that plaque will be present on the smooth surfaces of the tooth due to contact/rubbing with cheeks and tongue. Subjects will be stratified by their Day 0 pre-brushing RPI score (*lower*: mean RPI_{gingival/interproximal} ≥ 0.6 to ≤ 0.8 ; *higher*: mean RPI_{gingival/interproximal} > 0.8 to 1.0) to ensure treatment groups are balanced for baseline supra-gingival plaque levels.

A systematic review of manual toothbrush studies (59 publications with a total of 212 brushing exercises) reported 30–53% plaque removal after a single brushing occasion (depending on the clinical index used) and concluded that bristle tuft arrangement and duration of use contributed to the plaque removal efficacy of a brush. Four marketed manual toothbrushes with differing brush head designs, and therefore anticipated differences in cleaning performance, have been selected for evaluation. The dental profession typically recommend ≥ 2 minutes brushing at least twice daily for good oral hygiene, however, studies reported in the scientific literature indicate brushing duration to be much shorter (working estimate 45 seconds) ([Gallagher et al. 2009](#)). A 1 minute brushing time has been selected for this study as representative of consumer behavior.

The study toothbrushes differ in visual appearance. The level of blindness for this study is therefore described as 'examiner-blind'. Study toothbrushes will be dispensed by trained site personnel who are not involved in clinical efficacy assessment procedures and used by study subjects in the clinical examination area and the examiner won't be allowed in the room during this period. This will ensure the clinical examiner remains blinded to treatment and so avoid bias in the clinical assessments. Clinical examination and product usage areas will be free from mirrors to minimize the visual impact of disclosed plaque on subject brushing behavior.

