4.4.1 Primary Efficacy Endpoint

4.4.1.1 Primary Efficacy Endpoint Definition

The main focus of the analysis will be the ability of each study toothbrush to reduce supra-gingival plaque after first use (Day 0, pre- to post-brushing), as measured by mean RPI overall and mean TPI overall.

For RPI, each tooth surface is divided into nine zones (A to I); A-C along the gingival margin; D-F directly above A-C (D and F being the inter-proximal zones); G-H across the middle of the tooth and I covers the incisal area. The plaque will be disclosed and the presence or absence of plaque in each zone recorded, generating a total of 18 scores per tooth. RPI scale is described in [Table 4-2](#) below.

Table 4-2 RPI Scoring

Score	Description
0	Plaque absent
1	Plaque present

For TPI, each tooth surface is divided into 3 areas; three scores are recorded facially (mesiofacial, facial, distofacial) and three scores lingually (mesiolingual, lingual and distolingual) generating a total of six scores per tooth.

The plaque will be disclosed and scored for each site as described in [Table 4-3](#).

Table 4-3 TPI Scoring

Score	Description
0	No plaque
1	Slight flecks of plaque at the cervical margin of the tooth
2	Thin, continuous band of plaque (1 millimetre (mm) or smaller) at the cervical margin of the tooth
3	Band of plaque wider than 1mm but covering less than 1/3 of the area
4	Plaque covering at least 1/3 but less than 2/3 of the area
5	Plaque covering 2/3 or more of the crown of the tooth

Mean RPI_{overall} and mean TPI_{overall} will be calculated for each subject as the total score for all tooth sites assessed divided by the total number of tooth sites assessed.

Change from baseline will be derived for each individual tooth site first before calculating the mean overall change for all sites assessed. Changes from baseline will be derived, summarized and analyzed.

Descriptive statistics (n, missing, mean, SD, standard error [SE], median, minimum, and maximum values) of the pre-brushing, post-brushing and change from Day 0 pre-brushing in mean RPI_{overall} and mean TPI_{overall} scores will be presented in [Table 14.2.2.1.1](#) for mean RPI_{overall} and in [Table 14.2.2.2.1](#) for mean TPI_{overall} for all subjects in mITT population by study product group.

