4.5.1 Efficacy (Secondary)

The secondary efficacy endpoints are:

- Mean RPI_{overall} (Day 7 pre- and post-brushing, Day 28 pre- and post-brushing)
- Mean TPI_{overall} (Day 7 pre- and post-brushing, Day 28 pre- and post-brushing)
- Mean RPI_{gingival margin} (Day 0 pre- and post-brushing, Day 7 pre- and post-brushing, Day 28 pre- and post-brushing), defined as mean RPI score for sites A, B and C
- Mean RPI_{inter-proximal} (Day 0 pre- and post-brushing, Day 7 pre- and post-brushing, Day 28 pre- and post-brushing), defined as mean RPI score for sites D and F
- Mean TPI_{inter-proximal} (Day 0 pre- and post-brushing, Day 7 pre- and post-brushing, Day 28 pre- and post-brushing), defined as mean TPI score for mesial and distal sites

Secondary outcome variables will be derived, based on relevant tooth sites, as the primary outcome variables.

Summary statistics (n, missing, mean, SD, SE, median, minimum, maximum) of pre-brushing, post-brushing and change from Day 0 pre-brushing will be presented for each secondary outcome variable at each assessment time point by study product group in the following tables:

- [Table 14.2.2.1.1](#) for mean RPI_{overall}
- [Table 14.2.2.2.1](#) for mean TPI_{overall}
- [Table 14.2.2.3.1](#) for mean RPI_{gingival margin}
- [Table 14.2.2.4.1](#) for mean RPI_{inter-proximal}
- [Table 14.2.2.5.1](#) for mean TPI_{inter-proximal}

Change from baseline of secondary efficacy variables will be analyzed using ANCOVA model with product group as a fixed effect and the appropriate baseline value as a covariate, as defined below:

- For mean RPI_{overall}: baseline mean RPI_{overall}
- For mean TPI_{overall}: baseline mean TPI_{overall} and RPI stratification level (lower/higher)
- For mean RPI_{gingival margin}: baseline mean RPI_{gingival margin}
- For mean RPI_{inter-proximal}: baseline mean RPI_{inter-proximal}
- For mean TPI_{inter-proximal}: baseline mean TPI_{inter-proximal} and RPI stratification level (lower/higher)

Change from Day 0 pre-brushing to each analysis time points (Visit 2 Day 0 post-brushing, Visit 3 Day 7 pre- and post-brushing and Visit 4 Day 28 pre- and post-brushing) will be summarized for each secondary outcome variable by product group (adjusted mean change, percent change from mean baseline, 95% CIs and p-value for change from zero) in the following analysis tables:

- [Table 14.2.2.1.2](#) for mean RPI_{overall}
- [Table 14.2.2.2.2](#) for mean TPI_{overall}

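### A single RPI kappa over all nine zones and both brushing phases can reach the 0.6 mark for good repeatability with poor within-zone agreement, so zone-group kappas should be added

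*SAP*

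**What the plan says.** SAP 4.7, matching Protocol 12.3.8, sets out the examiner repeatability analysis: "The first and repeat plaque assessments on each tooth site will be cross tabulated". "A weighted kappa coefficient" with a 95% CI follows, and "Fleiss-Cohen weighted kappa will be calculated for the repeatability analysis". Values above 0.75 are called excellent, 0.4 to 0.75 fair to good, and below 0.4 poor. A kappa of at least 0.6 "will be considered indicative of good repeatability across the study period". "Results for RPI scoring repeatability will be presented in" one table, 14.2.3.1. Repeats alternate between pre- and post-brushing assessments.

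RPI is binary: SAP 4.4.1.1 has "the presence or absence of plaque in each zone recorded, generating a total of 18 scores per tooth", from nine zones on each of two surfaces. Randomized subjects need a Day 0 pre-brushing mean of at least 0.6 over zones A, B, C, D and F. Protocol 4.2 gives the reason: "Interproximal and gingival margins were chosen due to the unlikelihood that plaque will be present on the smooth surfaces of the tooth". The primary RPI endpoint uses all sites. Two secondary RPI endpoints use subsets: gingival margin, "defined as mean RPI score for sites A, B and C" (SAP 4.5.1), and inter-proximal, sites D and F.

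**The concern.** Kappa compares observed agreement with the agreement expected if every site shared one overall prevalence. Pooling zones that are usually positive with zones that are usually negative makes that expected agreement too low for each zone separately. Two readings that merely follow the typical pattern of the zones, and the typical drop after brushing, then earn a kappa well above zero. The Fleiss-Cohen weights do not change this, because on a 0/1 score weighted and unweighted kappa are the same.

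At stake is what may be said about gingival-margin and inter-proximal RPI. Both are separate endpoints in a study meant to inform the methods of later trials. Repeatability could be labelled good while agreement inside those zones is poor by the plan's own bands, and no described output would show it.

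**Working it through.** There is no computed figure in the plan to reproduce; 0.6 is a criterion. The check asks what pooled kappa results from a given agreement within zones.

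**Inputs from the documents.** Five zones (A, B, C, D, F) and four others (E, G, H, I); pre-brushing mean at least 0.6 in the five for entry; repeats alternating by phase; 30-53% plaque removal in one brushing (Protocol 2.1).

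**Assumptions.** Pre-brushing prevalence p1 in the five zones (0.60 to 0.90) and p0 in the other four (0.05 or 0.10). Pre- and post-brushing repeats in equal numbers. A 40% reduction in every zone. Equal prevalence on first and repeat reading. The same kappa, kw, inside each combination of zone group and phase (called within-zone below).

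**Formula.** With cell prevalences p and cell shares w, let pbar = sum(w p), M = sum[w p(1-p)] and V = pbar(1-pbar). Observed agreement is 1 - 2(1-kw)M and expected agreement is 1 - 2V, so

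pooled kappa = 1 - (1-kw) M/V.

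**Worked case, p1 = 0.80, p0 = 0.05.** Post-brushing prevalences are 0.48 and 0.03.
- pbar = (5×0.80 + 4×0.05 + 5×0.48 + 4×0.03)/18 = 6.72/18 = 0.3733
- M = (5×0.16 + 4×0.0475 + 5×0.2496 + 4×0.0291)/18 = 2.3544/18 = 0.1308
- V = 0.3733×0.6267 = 0.2340, so M/V = 0.559
- kw = 0 gives 1 - 0.559 = 0.44; kw = 0.3 gives 1 - 0.7×0.559 = 0.61

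**Same calculation elsewhere.** The last column is 1 - 0.4/(M/V), the within-zone kappa at which the pooled value reaches 0.6.

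| p1 | p0 | Zone E | Pooled, kw = 0 | Pooled, kw = 0.3 | kw needed |
|---|---|---|---|---|---|
| 0.80 | 0.05 | as p0 | 0.44 | 0.61 | 0.28 |
| 0.85 | 0.05 | as p0 | 0.49 | 0.64 | 0.22 |
| 0.90 | 0.05 | as p0 | 0.54 | 0.68 | 0.12 |
| 0.80 | 0.10 | as p0 | 0.39 | 0.57 | 0.35 |
| 0.90 | 0.10 | as p0 | 0.49 | 0.64 | 0.22 |
| 0.70 | 0.05 | as p0 | 0.35 | 0.55 | 0.38 |
| 0.60 | 0.05 | as p0 | 0.27 | 0.49 | 0.45 |
| 0.60 | 0.10 | as p0 | 0.23 | 0.46 | 0.48 |
| 0.80 | 0.05 | 0.5 | 0.37 | 0.56 | 0.36 |
| 0.90 | 0.05 | 0.5 | 0.47 | 0.63 | 0.25 |

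Varying the reduction over 30-53% moves the first three rows little: 0.44 to 0.56 at kw = 0, and 0.61 to 0.69 at kw = 0.3.

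**Pre-brushing repeats only**, kw = 0: p1/p0 of 0.85/0.05 gives 0.63, 0.90/0.05 gives 0.71 and 0.90/0.10 gives 0.64.

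**Why phase matters too.** Collapsing A, B, C, D, F over phases with kw = 0.3 gives 0.38, 0.39 and 0.41 at p1 = 0.80, 0.85 and 0.90. The drop after brushing therefore lifts even a zone-group kappa above 0.3.

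**The case against.** Several points on the other side stand.

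- A reader might infer that zone differences alone take kappa to 0.6-0.7. The documents do not support that. It needs pre-brushing repeats only and high assumed prevalence, whereas the plan alternates phases; in the mix, the three scenarios just listed fall to about 0.49 to 0.54. Some real agreement is needed as well, though it may be poor.
- The prevalences are not known. The documents give a floor of 0.6 for five zones and a qualitative remark about smooth surfaces. One whole stratum lies at 0.6 to 0.8, and zone E sits between the two inter-proximal zones.
- The pooled kappa fits the primary RPI endpoint, which uses all nine zones. Only the secondary RPI endpoints are confined to A-C or D/F.
- Pooling is inferred from a single kappa and a single table; the table layout is not available to check.
- Repeatability is exploratory. Study success rests on a numerical plaque reduction, and no action depends on the 0.6 label. The examiner must also have shown repeatability beforehand.
- A reader might also infer that the RPI-versus-TPI choice is distorted. No comparison of the two kappas is planned, and no TPI calculation has been made here.
- Moving the 0.6 cut-off onto zone groups would create the opposite problem. At prevalence 0.90, expected agreement is 0.81 + 0.01 = 0.82, so 92% raw agreement gives (0.92 - 0.82)/0.18 = 0.56. At 0.95, expected agreement is 0.905, so 95% raw agreement gives 0.045/0.095 = 0.47. A consistent examiner could fail.

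These points limit the size and the remedy. They do not answer the gap: nothing described shows agreement within the zones of the secondary endpoints.

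**Conclusion.** The point holds in a limited form. Under the natural reading of SAP 4.7, differences between zones and phases raise the RPI kappa. With prevalence 0.80 to 0.90 in A, B, C, D, F and 0.05 elsewhere, they contribute about 0.44 to 0.54, and a within-zone kappa of 0.3 is then reported as about 0.61 to 0.68, which the plan would call good. The result depends on those assumptions. At prevalence 0.70 or less, or with zone E at 0.5, the same agreement gives about 0.46 to 0.63 and mostly falls short of 0.6. The documents cannot settle which case applies. This does not touch the primary analysis. It limits what a pooled kappa can support for the gingival-margin and inter-proximal endpoints, and it is a cheap improvement to make.

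**What to change.** In SAP 4.7 and Table 14.2.3.1:

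- Keep the pooled RPI kappa and state explicitly that it covers all zones and both phases.
- Add RPI kappa with 95% CI, and raw percent agreement, for A-C, D/F and E/G/H/I, each by pre- and post-brushing phase.
- State that good repeatability for the gingival-margin and inter-proximal endpoints will not be concluded from the pooled kappa alone, but from the zone-group kappas read together with raw agreement.
- Do not simply transfer the 0.6 cut-off to the zone groups.

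Scores are already recorded by zone, so the cost is SAP wording and extra table rows. The downside is that zone-group kappas are less precise and can be low when prevalence is near 1, which is why raw agreement must stand beside them.

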9.2.4 Repeatability Assessments

The clinical examiner selected for this study will have demonstrated their ability to replicate their own scores (intra-examiner repeatability) on a tooth site-by-tooth site basis in previous studies and/or calibration exercises. Given both the RPI and the TPI allow accurate repeat assessment, repeat assessments will be performed for both clinical measures throughout the treatment period (Visits 2-4) to monitor consistency of scoring.

One repeat assessment will be completed for each clinical index on each clinical assessment day (one in the morning, one in the afternoon), alternating between pre- and post-brushing assessments for each index (plaque will be disclosed as described in [Section 9.2.1](#)).

Repeatability assessments should be separated by a minimum of 10 minutes and, where possible, the clinical examiner should assess a different subject in the intervening period. The examiner should not have sight of their previous scores when carrying out a repeat assessment.

‘Repeat’ subjects will be selected from those in attendance on a particular study day.

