12.3.8 Repeatability Analyses

The repeat dental plaque assessments will be compared to the original assessments; repeat assessments will not be used in any efficacy analyses. The first and repeat plaque assessments on each tooth site will be cross tabulated. A weighted kappa coefficient (κ), along with the 95% CI will be calculated to assess the intra-examiner reliability. Fleiss-Cohen weighted kappa will be calculated for the repeatability analysis. Reliability will be deemed

- excellent if $\kappa > 0.75$;

Property of GSK Consumer Healthcare - Confidential

May not be used, divulged, published or otherwise disclosed without the consent of GSKCH

SP1963/SOP-208661: Template Version: 14 Mar 2019

- fair to good if $0.4 \leq \kappa \leq 0.75$;
- poor if $\kappa < 0.4$.

A $\kappa \geq 0.6$ will be considered indicative of good repeatability across the study period. All subjects who have repeatability data will be included in this analysis.

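### The only repeatability test, site-level kappa of 0.6 or more, can pass a one-directional scoring shift; a signed first-to-repeat difference in mean score should be reported beside it

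*SAP*

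**What the plan says.** **Repeatability.** SAP 4.7 works at tooth-site level: "The first and repeat plaque assessments on each tooth site will be cross tabulated". Protocol 12.3.8 states that "Fleiss-Cohen weighted kappa will be calculated for the repeatability analysis", and SAP 4.7 repeats this. Both give bands (excellent above 0.75, fair to good from 0.4 to 0.75, poor below 0.4), and both add that a kappa of at least 0.6 "will be considered indicative of good repeatability across the study period". Repeats are taken at Visits 2 to 4, "alternating between pre- and post-brushing assessments for each index". Under Protocol 9.2.4, "Repeatability assessments should be separated by a minimum of 10 minutes". Neither document plans a signed difference, a marginal-homogeneity test or a subject-level agreement statistic, and SAP Table 5-1 adds none.

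**Endpoints.** In SAP 4.4.1.1 the mean scores are "calculated for each subject as the total score for all tooth sites assessed divided by the total number of tooth sites assessed". The ANCOVA analyses take the signed change in these means from Day 0 pre-brushing and test each brush against zero (SAP 4.4.1.2 and 4.5.1).

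**Scales.** RPI is binary, with "the presence or absence of plaque in each zone recorded, generating a total of 18 scores per tooth". TPI has six levels from 0 to 5, the top one being "Plaque covering 2/3 or more of the crown of the tooth".

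**The concern.** The statistic that certifies the measurement differs in kind from the statistic that is analysed. Kappa sets site-by-site disagreement against the spread of site scores. With Fleiss-Cohen weights on a 0-5 scale, a one-category disagreement is charged only 1/25 of the maximum. The analysed endpoints are averages over many sites. Random site errors largely cancel in such an average, but an error in one direction does not. The pass rule cannot tell the two apart.

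This matters because the study exists to develop a measurement method, so a statement that repeatability was good is one of its outputs. The primary contrast is a within-brush change over two readings at one visit. If the examiner's stringency moves between successive readings, that change moves with it, and a within-brush test has no between-arm contrast to cancel it.

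**Working it through.** The plan has no figure to reproduce: 0.6 is a chosen criterion. The documents give no TPI site distribution, site SD, baseline mean or expected change in points. The site distributions and baselines below are therefore assumptions, shown over a range.

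**1. TPI, formula.** Quadratic weighted kappa is 1 minus the observed mean squared difference divided by that expected under independence. Suppose a fraction *f* of sites, chosen independently of score, is read one category higher the second time, with no other error and no ceiling.

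- Observed mean squared difference: *f*
- Expected: SD² + [SD² + *f*(1−*f*)] + *f*² = 2·SD² + *f*
- kappa = 1 − *f*/(2·SD² + *f*) = SD²/(SD² + *f*/2)

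Break-even with 0.6:

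- Full shift (*f* = 1): SD² = 0.75, SD = 0.87
- Half shift (*f* = 0.5): SD² = 0.375, SD = 0.61

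**2. TPI with the ceiling.** A site already scored 5 cannot rise, so the tables were recomputed with a cap at 5, for rounded-normal site scores with means 1.5 to 3.

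| Observed site SD | Full shift: kappa | Half shift: kappa |
|---|---|---|
| about 0.57 | 0.39-0.41 (fails) | about 0.57 (fails) |
| about 0.75 | 0.52-0.53 (fails) | 0.69-0.70 (passes) |
| about 0.85 | 0.58-0.59 (fails) | about 0.74 (passes) |
| 0.92-1.35 | 0.62-0.78 (passes) | 0.77-0.88 (passes) |

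In the rows that pass, the mean moves by about 0.9 to 1.0 points (full) or 0.43 to 0.50 points (half).

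**3. Added random error.** With mean 2.5 and latent SD 0.9, random ±1 errors on 20% of sites lower the full-shift kappa from 0.63 to 0.59, which fails. With latent SD 1.2 it goes from 0.735 to 0.70, which passes.

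**4. Pooling pre- and post-brushing repeats.** One results table per index is planned, and pooling widens the spread. With latent SD 0.7, a full shift gives 0.53 at mean 2.5 alone and 0.53 at mean 1.5 alone. Mixed equally (pooled SD 0.90), the same shift gives 0.62.

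**5. RPI.** With two levels the weights have no effect. For a one-way move in prevalence from p1 to p2, po = 1 − (p2 − p1), pe = p1·p2 + (1−p1)(1−p2) and kappa = (po − pe)/(1 − pe).

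- 0.40 to 0.55: (0.85 − 0.49)/(1 − 0.49) = 0.71
- 0.40 to 0.60: (0.80 − 0.48)/(1 − 0.48) = 0.615
- 0.30 to 0.50, or 0.50 to 0.70: (0.80 − 0.50)/(1 − 0.50) = 0.600
- 0.20 to 0.40, or 0.60 to 0.80: (0.80 − 0.56)/(1 − 0.56) = 0.545

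A shift of 0.20 thus reaches 0.6 only from a starting prevalence of 0.30 to 0.50. Its kappa is lower still at more extreme prevalences than those listed.

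**6. Scale of the brushing effect.** Protocol 2.1 cites 30-53% removal after one brushing, depending on the index.

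- Assumed TPI of 2.2: 0.30 × 2.2 = 0.66 to 0.53 × 2.2 = 1.17 points
- Assumed RPI of 0.5: 0.30 × 0.5 = 0.15 to 0.53 × 0.5 = 0.27

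**7. One threshold, two scales.** Take two readings with latent correlation 0.80 and no shift. A binary score split 50/50 gives (2/π)·arcsin(0.80) = 0.59, just below 0.6. Simulated six-level scores (means 2 to 2.5, latent SD 0.7 to 1.2) give quadratic kappa of about 0.69 to 0.75.

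**The case against.** - **Kappa does respond.** From perfect agreement, a full TPI shift lowers it by 0.22 to 0.38 in the passing range, and at smaller site SD the rule catches the shift. A reader might infer that kappa ignores directional error, or that any one-category shift passes. The documents give no site SD and do not support that. This stands, and it is why the result is conditional.
- **The cross-tabulation would show it.** A uniform TPI shift appears as an off-diagonal band. This stands: the information is not hidden. But the pre-specified conclusion does not use it.
- **A constant stringency cancels in a pre-to-post change, and each repeat is compared with a reading in the same condition.** A reader might infer that a passing kappa conceals a known bias in the primary result, or that a signed difference would measure every such bias. Neither follows. The signed difference shows drift from first to second reading within a visit, a sequence similar to the one the primary change relies on, and no more.
- **Little depends on it formally.** Repeatability is exploratory, repeats stay out of the efficacy analyses, study success does not use kappa, and the examiner must have shown repeatability beforehand. This limits the point to a cheap improvement.
- **Index choice.** A reader might infer that the plan would rank RPI and TPI wrongly by their kappas. Nothing in the documents ranks them that way; Protocol 4.2 ties the choice to how well each index characterises plaque removal.
- **Study-period wording.** It can fairly mean pairs sampled over Visits 2 to 4, and needs no change.

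**Conclusion.** The point holds in conditional form. A kappa of 0.6 or more on sites does not by itself show that subject-level mean scores are free of a material one-directional shift, and the plan has no other repeatability statistic.

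The half-category TPI shift is the firmer case. It passes at every site SD examined from about 0.75 upward, and it equals roughly 0.4 to 0.75 of the assumed TPI brushing effect (0.43/1.17 = 0.37 to 0.50/0.66 = 0.76). The full-category shift passes only if the site SD is about 0.9 or more and other error is modest. On RPI, a shift equal to the lower end of the assumed effect (0.15) passes from a starting value of 0.40, while 0.20 is borderline and depends on prevalence.

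These sizes rest on assumed site distributions, an assumed TPI of 2.2 and an assumed RPI of 0.5. The removal range is a literature figure that is not split by index in the documents. No efficacy estimate is shown to be wrong.

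**What to change.** In SAP 4.7, Tables 14.2.3.1 and 14.2.3.2, beside kappa:

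1. For each repeated examination, compute the first and repeat subject-level means used as endpoints (RPI overall, gingival margin and inter-proximal; TPI overall and inter-proximal). Report the mean signed difference (repeat minus first) with 95% CI and limits of agreement, with pre- and post-brushing examinations shown separately.
2. Express the signed difference relative to that index's Day 0 pre- to post-brushing change.
3. Conclude good repeatability only when kappa is at least 0.6 and the signed difference is small. The sponsor should set what counts as small before unblinding.
4. Do not compare RPI and TPI reliability by their kappas, because 0.6 means different reliability on the two scales.
5. State the limit: the signed difference detects drift from first to second reading within a visit. It does not detect drift between visits, or bias from knowing that a reading is post-brushing.

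The cost is SAP text and a few rows in two existing tables, with no new data. The repeatability statement may become less favourable. The number of repeats depends on the number of assessment days, which the documents do not give, so the split intervals may be wide and should be read as such.
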